A feared complication after total hip arthroplasty (THA) is prosthetic joint infection (PJI), associated with high morbidity and mortality (1-3). Perioperative antimicrobial prophylaxis is a well-established and documented part of standard care to reduce the risk of PJI after THA(4-6). There is however no consensus regarding duration of prophylaxis. Danish national guidelines recommend both one single pre operative dose as well as 24 hours of antibiotic coverage as strategies for antibiotic prophylaxis practice, i.e. a single preoperative dose or a 24 hour coverage using either cloxacillin or the second-generation cephalosporin, cefuroxime(7). The choice of antibiotic agent as well as duration, varies among the different orthopedic departments in Denmark which also reflects the clinical practice internationally.

Antimicrobial resistance poses a persistent and increasing global healthcare problem due to its limited treatment options. In addition, patients may experience systemic toxicity following prolonged use of antibiotics (8-12). Therefore, there is a need for optimizing the use of antibiotics and a reduction would be beneficial, but is should be without risking more infections. No randomized trial has compared one single preoperative dose with 24 hours of antibiotic coverage in THA. This comparison is important to establish best evidence-based practice on antibiotic prophylaxis dosages in the future and combating antimicrobial resistance.

Objectives

The primary objective of this trial is to compare the effect of single versus multiple prophylactic antibiotic doses administered within 24 hours of primary THA due to osteoarthritis on risk of revision due to PJI within 90 days. The noninferiority of single prophylactic antibiotic would be shown if the upper boundary of the two-sided 95% confidence interval for the Odds Ratio is less than 1.4 for the single prophylactic doses as compared with multiple prophylactic antibiotic doses.

Key secondary objectives

To compare the effect of single versus multiple prophylactic antibiotic doses administered within 24 hours of primary THA due to osteoarthritis on critical outcomes assessed up to 90 days from surgery: Serious Adverse Events (SAEs), Potential PJI referred to as *PJI-likely*, Length of stay for hospitalization (LOS), Major Adverse Cardiovascular Events, Hospital-treated infections (Other

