Choice of the non-inferiority design will enable the deliverance of substantial evidence to change clinical practice if the prevention of PJI with a single dose of prophylactic antibiotic is “no less effective than” antibiotic practices of longer duration (i.e., multiple doses). Members of the Danish orthopedic community have been involved in deciding the potentially increased serious infection rate difference, we are willing to tolerate. Because the sample size is based on the standard flow of THA within the Danish real-world setting, we did not conduct formal power or sample size calculations. Initially, we defined “appreciably worse” serious infection rates and the chances of an erroneously significant result, that is, a false positive, that the medical community will tolerate. The PJI rate in Denmark is between 0.5% and up to 5,1%, (mean 1,2%; 95% CI: 1,0-1,4) varying at departmental level (21). It was decided that we will be willing to tolerate a potentially increased serious infection risk difference of up to 0.1% (1‰ more having a PJI i.e., up to one per thousand).

Confidence intervals and p-values

All 95% confidence intervals (95%CIs) and *P*-values will be two sided. We will not apply explicit adjustments for multiplicity, rather we will interpret the key secondary endpoints with caution.

Primary endpoint: If we assume that the PJI risk is similar in the two groups (with 10,000 patients in each) we expect to achieve a precision (narrowness) in the two-sided 95% confidence intervals around the Odds Ratio (OR=1.000) from a Generalized Linear Mixed Model (GLMM), with 95% limits from 0.756 to 1.323; with a Random Effects factor for the 36 individual centers, and Fixed Effect factors for group, period and the interaction between group and period (Group \times Period). This was validated through multiple simulations. The same simulations were carried out with a population of 8,000 in each group for sensitivity, resulting in 95 % limits around the Odds Ratio (OR=1.000) from 0.731 to 1.368. Based on the CIs from these simulations, that

have very little variability, and the clinical importance of PJIs, a pragmatic non-inferiority margin should be chosen. Thus, non-inferiority will be shown if the upper limit of the two-sided 95% confidence interval for the odds ratio (derived from the GLMM) is less than 1.4 for the single dose as compared with the multiple doses group.

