In addition to the simulations, a bootstrap analysis of 1,000 iterations using the 10,000-patient simulation yielded a 95% confidence interval from 0.763 to 1.374. The proximity of the bootstrap result (1.374) to the proposed margin (1.4) demonstrates that the margin accommodates the variability in the trial design while maintaining sufficient statistical power and clinical importance.

With this approach, we anticipate that the results of this cluster randomized, cross-over, non-inferiority trial will generate high-quality evidence that may advance and inform clinical practice on antibiotic prophylaxis dosages in the future.

Statistical interim analysis and stopping guidance

No statistical interim analysis was planned on any endpoint (index surgery to 90-day follow-up) between the two groups (i.e., single-dose and multiple-dose) between the two groups (single-dose and multiple-dose), as it was assessed that there would not be sufficient statistical power to conduct a meaningful interim analysis. Performing such an analysis could lead to premature conclusions, posing ethical concerns regarding participant safety and treatment efficacy. Therefore, no interim analysis was planned to uphold our study's scientific integrity and ethical responsibility. The final deadline for patient recruitment was set to 30. November 2024, corresponding to a 2-year study period for the departments that started patient inclusion as of December 1st, 2022.

Timing of final analysis

The final analysis for the between-group comparison (Single-dose vs. Multiple) for the primary endpoint (index surgery to 90-day follow-up) is planned to be performed after each randomized patient has completed the 90-day follow-up, corresponding to March 1st, 2025. The main publication of the trial will be prepared when these data have been received and cleaned. The data is anticipated to be received by May 2025 and the cleaning completed by July 2025. In subsequent manuscripts including exploratory outcomes, secondary longer-term endpoints will be analyzed when the 12 months (corresponding to March 2026) and 60 months (March 2030) has been reached

for all randomized patients followed by preparation of manuscripts with one and five-year outcomes, respectively.

Timing of secondary outcome assessments

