The primary analyses will be based on the Intention to Treat (ITT) population, i.e., all patients undergoing the prespecified surgery corresponding to the specific year (cross-over, cluster randomization). Two-sided 95% confidence intervals will be estimated and reported enabling (standard) superiority interpretations. The primary statistical analysis model will be based on a *Generalized Linear Mixed Model*, with a random effects factor applied indexing the clinical center (36 levels: 1, 2, 3, ..., up to 36), a fixed effect will be applied for period (2 levels: 1st and 2nd year, respectively), and antibiotics group (2 levels: Single-dose and Multiple-dose, respectively), as well as the interaction between the two period and antibiotics group (period×group; 4 levels: 2×2 levels). For the primary endpoint: Noninferiority will be shown if the upper limit of the two-sided 95% CI for the odds ratio is less than 1.4 for the single antibiotic doses as compared with multiple doses.

In addition, subgroup analyses will be performed to examine the following known and suspected baseline risk factors for PJI infection will be compared: age (≥ 65 versus < 65 years), sex (male versus female), Anthropometric categories (BMI: ≥ 30 versus $< 30 \text{ kg/m}^2$) as well as morbid obesity (BMI: ≥ 40), and presence of diabetes (with versus without). Additional analyses of the study will assess whether the difference of PJI risk in the two treatment arms differ in specific subsets of patients: femoral stem cementation (antibiotic-loaded bone cement versus bone cement with no antibiotic-load and cementless fixation vs fixation with bone cement) and type of antibiotic (beta-lactam antibiotics versus other). The rationale for these analyses is that we suspect the risk of infection to be different in these subgroups. The pharmacokinetics of the antibiotics might have an impact on the infection rates in the relevant groups. The statistical approach for this evaluation of potential effect modifiers is a test for statistical interaction to evaluate whether the treatment effect varies across levels of the effect modifier (46).

Finally, blinded results from the statistical analyses (single-dose compared to multiple-dose) will be presented to the author group followed by development of two written interpretations. The author group will sign a consensus statement comprising both interpretations prior to the unsealing of the randomization code.(47)

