Outcome	Single-dose (N =)	Multiple- dose (N =)	Odds Ratio (95% CI)	†Absolute risk difference (95%CI)
Primary Outcome				
Prosthetic Joint infection at 90 days, no. (%)				
Key Secondary Outcomes				
Serious adverse events (SAE), no. (%)				
PJI-likely, no. (%)				
Major Adverse Cardiovascular Events, no. (%)				
Length of stay (LOS), days				
Hospital-treated infections (excluding SSI), no. (%)				
Community-based antibiotic use, no. (%)				
Opioid use, no. (%)				
Use of acetaminophen/non-steroidal anti-inflammatory drugs , no. (%)				
Revision due to any cause, no. (%)				

* The primary analyses will be based on the Intention to Treat (ITT) population based on the Full Analysis Set; i.e., all patients undergoing the prespecified surgery using the antibiotic dose corresponding to the specific year (cross-over, cluster randomization). Two-sided 95% confidence intervals will be estimated and reported enabling (standard) superiority interpretations. The primary statistical analysis model will be based on a *Generalized Linear Mixed Model*, with a random effects factor applied indexing the clinical center (36 levels: 1, 2, 3, ..., up to 36), a fixed effect will be applied for period (2 levels: 1st and 2nd year, respectively), and antibiotics group (2 levels: Single-dose and Multiple-dose, respectively), as well as the interaction between the two (period×group; 4 levels: 2×2 levels). Hierarchical models account for variations in baseline risk across clusters (e.g., sites or patient subgroups). †Absolute risk differences and their 95% confidence intervals will be derived from odds ratios and corresponding 95% confidence intervals estimated by the hierarchical model, incorporating the baseline risk in the reference group (multiple-dose). The 95% confidence intervals will not be adjusted for multiplicity and should not be used in place of hypothesis testing.

Table 3. Serious Adverse Events within 90 days within each group. *

Events	Single-dose (N =)	Multiple-dose (N =)	Odds ratio (95% CI)	Absolute risk difference [†]
Serious adverse event — no. (%)				
Any infection requiring intravenous antibiotics				
Severe allergic reaction				
Organ failure				
Life-threatening events				
Musculoskeletal				
Deep infection				
Hip dislocation				
Femoral fracture				
Aseptic loosening				
Cardiovascular				
Vascular injury				
Pulmonary embolism				
Deep venous thrombosis				
Acute myocardial infarction				
Stroke				
Nervous system				
Nerve injury				

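### The OR 1.4 non-inferiority margin is worth about +0.47 percentage points at the SAP's mean PJI risk of 1.2%, 4.7 times the 0.1% increase it calls tolerable, and nothing links the two

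*SAP*

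**What the plan says.** Under Sample size and power calculation, the SAP describes how the acceptable loss was agreed: "Members of the Danish orthopedic community have been involved in deciding the potentially increased serious infection rate difference". The outcome was that "we will be willing to tolerate a potentially increased serious infection risk difference of up to 0.1"%, which the SAP restates as one per thousand. The figure is therefore absolute, and it is not a slip for 1%. The same paragraph gives a national PJI rate with mean 1.2% (95% CI 1.0 to 1.4) and a departmental range of 0.5% to 5.1%.

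The test uses another scale. Objectives requires that the "upper boundary of the two-sided 95% confidence interval for the Odds Ratio is less than 1.4 for the single prophylactic doses". Confidence intervals and p-values and Analysis methods repeat the same rule; the latter says "Noninferiority will be shown if the upper limit of the two-sided 95% CI for the odds ratio is less than 1.4".

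The grounds given for 1.4 are the simulated intervals around an odds ratio of 1 (0.756 to 1.323 with 10,000 per group, 0.731 to 1.368 with 8,000). The SAP reasons that because these "have very little variability, and the clinical importance of PJIs, a pragmatic non-inferiority margin should be chosen". It adds that "The proximity of the bootstrap result (1.374) to the proposed margin (1.4) demonstrates that the margin accommodates the variability in the trial design". The 0.1% does not appear in this argument.

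In the Table 2 footnote, "Absolute risk differences and their 95% confidence intervals will be derived from odds ratios and corresponding 95% confidence intervals", using the baseline risk of the multiple-dose group. No threshold is attached to those differences.

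**The concern.** Which test to run is not in doubt: the odds-ratio rule is the same everywhere. The difficulty is what a pass would mean. The SAP records one absolute statement of acceptable harm, says the orthopedic community took part in deciding it, and then tests against a margin that is several times wider at any PJI rate close to its own mean. A margin should come from the loss that is tolerable. Here it is supported by the precision the trial expects to reach, together with an unquantified appeal to clinical importance.

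This is the primary decision rule of a trial intended to change practice. A reader who sees a declaration of non-inferiority next to a one-per-thousand tolerance could take the second to have been shown by the first.

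**Working it through.** **Inputs (all from the SAP).** Margin OR 1.4; two-sided 95% CI; tolerance 0.001; mean PJI risk 0.012 (0.010 to 0.014); lowest departmental rate 0.005; 10,000 per group; expected limits 0.756 to 1.323.

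**1. The SAP's own precision.** Expected limits at OR = 1 are exp(±1.96 × √(2/(n·p·(1−p)))).
- n = 10,000, p = 0.010: SE 0.1421, limits 0.757 to 1.321, which match the stated 0.756 to 1.323.
- n = 8,000, p = 0.010: limits 0.732 to 1.365, against the stated 0.731 to 1.368.
- n = 10,000, p = 0.012: SE 0.1299, limits 0.775 to 1.290.

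The stated intervals thus correspond to a PJI risk of about 1.0%, the lower end of the SAP's interval. The SE they imply is (ln 1.323 − ln 0.756)/3.92 = 0.1428.

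**2. The margin as a risk difference.** With o = p0/(1−p0), p1 = 1.4·o/(1 + 1.4·o) and RD = p1 − p0. This is the kind of conversion the Table 2 footnote plans. At 1.2%, p1 = 1.672%, so RD = 0.472 points.

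| Baseline risk | OR 1.4 as RD | Multiple of 0.1 points | OR equal to +0.1 points |
|---|---|---|---|
| 0.5% | 0.199 points | 2.0 | 1.201 |
| 1.0% | 0.394 points | 3.9 | 1.101 |
| 1.2% | 0.472 points | 4.7 | 1.084 |
| 1.4% | 0.549 points | 5.5 | 1.073 |

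Solving RD = 0.001 at OR 1.4 gives p0 = 0.25%.

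**3. Chance of passing when the true excess is above the tolerance.** Pass probability = Φ((ln 1.4 − ln OR)/SE − 1.96), with 10,000 per group. The Wald SE is √(1/(n·p0·(1−p0)) + 1/(n·p1·(1−p1))), without a clustering term; the alternative is the SAP-implied 0.1428.

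| Baseline | True excess | Wald SE | SAP-implied SE |
|---|---|---|---|
| 1.2% | 0.1 points | 52% | 43% |
| 1.2% | 0.2 points | 30% | 24% |
| 1.2% | 0.3 points | 14% | 12% |
| 1.2% | 0.47 points | 2.5% | 2.5% |
| 1.0% | 0.2 points | 20% | 19% |
| 1.0% | 0.3 points | 8% | 7% |

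A true excess equal to the margin passes only at the ordinary 2.5% error rate. The gap concerns excesses between 0.1 points and the margin.

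**4. What equal arms would show.** The SAP's expected upper limit of 1.323 converts to +0.32, +0.38 and +0.44 points at 1.0%, 1.2% and 1.4%. Even identical risks would not be expected to exclude an excess of 0.1 points.

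**The case against.** The best defence is that the SAP never says the 0.1% bounds the confidence limit. If it is read as a limit on the observed difference, the two figures come close. The largest observed odds ratio that can pass is 1.4/exp(1.96 × 0.1428) = 1.058 with the SAP-implied precision, or 1.4/1.290 = 1.085 with the Wald precision at 1.2%. At 1.2% these are observed excesses of about 0.07 and 0.10 points. A passing trial of this size would therefore show an observed excess of roughly 0.1 points or less. That is true and a reader should know it. But the SAP does not state this reading, and bounding the estimate does not bound the true excess: an upper limit just under 1.4 leaves about 0.47 points compatible with the data at 1.2%.

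Three further points have weight.
- The 1.2% is a national rate. The SAP does not say it is the 90-day risk under multiple doses with this PJI definition. The 4.7 is therefore conditional, and at 1.0% it is 3.9. The direction holds at every rate the SAP gives.
- A 0.1-point margin was out of reach. With equal risks of 1.2%, 80% power and one-sided 0.025, it needs (1.96 + 0.8416)² × 2 × 0.012 × 0.988/0.001² ≈ 186,000 per group. This explains why a wider margin was used, but not why the 0.1% was left beside it unexplained.
- The SAP cites a separate protocol article, which may record how the 0.1% was later treated. The absence of a link is asserted for the SAP only.

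It is also fair that any non-inferiority test sometimes passes true effects inside its margin. The pass probabilities describe the size of the gap and are not a second fault.

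**Conclusion.** The concern holds. The SAP's decision threshold does not deliver the tolerance stated beside it. An odds ratio of 1.4 corresponds to +0.47 points at the SAP's mean risk, 4.7 times the tolerance; to 3.9 to 5.5 times over 1.0% to 1.4%; and to twice the tolerance even at the lowest departmental rate. At 1.2%, meeting the rule excludes an excess of about 4.7 PJIs per 1,000, not 1 per 1,000. True excesses of two to three times the tolerance would be declared non-inferior with a chance of about 12% to 30% at a 1.2% baseline (the range spans both precision assumptions), or about 7% to 20% at 1.0%.

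The conversion takes the SAP's national rate as the control risk and treats the centre-conditional odds ratio as if it were marginal, which matters little at such low rates. The pass probabilities are normal approximations. The finding that the margin exceeds the tolerance depends on none of the choices of baseline within the SAP's range. Because it affects what the primary result may claim, it must be settled before the results are interpreted.

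**What to change.** Before the randomization code is unsealed, and preferably before the author group signs its two blinded interpretations, the sponsor should reconcile the figures in a dated SAP addendum. Both stay on record and neither is silently replaced. The addendum should:

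1. State the absolute equivalent of OR 1.4 (+0.47 points at 1.2%; 0.39 to 0.55 points over 1.0% to 1.4%) beside the 0.1% tolerance, and say that they differ.
2. Disclose that 1.4 was chosen with regard to simulated and bootstrap interval width, and stop presenting that width as clinical justification.
3. Require any non-inferiority conclusion to quote the upper limit of the OR-derived absolute risk difference already planned for Table 2.
4. State that an upper limit below 1.4 does not by itself show that the 0.1% tolerance is met.

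The primary test is unchanged, and no new data, patients or analyses are needed. The price is a less favourable stated tolerance or a more limited conclusion. Because the tolerance was agreed with the orthopedic community and recruitment has closed, the reconciliation needs their input and a dated record, not just an edit of wording.

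### The SAP infers sufficient power from a bootstrap limit lying close to the 1.4 margin, but its own intervals imply only about 65% power (10,000 per group) or 56% (8,000 per group) at a true odds ratio of 1.0

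*SAP*

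**What the plan says.** Under *Sample size and power calculation* the SAP takes the sample size from the national flow of operations and states that "we did not conduct formal power or sample size calculations". It gives the Danish rate of prosthetic joint infection (PJI) as "mean 1,2%; 95% CI: 1,0-1,4".

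Under *Confidence intervals and p-values* it assumes equal risk in the two groups and reports simulated precision around an odds ratio of 1.000: "with 95% limits from 0.756 to 1.323" for 10,000 per group and "from 0.731 to 1.368" for 8,000 per group. Non-inferiority is declared if the upper limit of the two-sided 95% interval "is less than 1.4 for the single dose as compared with the multiple doses group".

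The next paragraph adds a bootstrap of 1,000 iterations on the 10,000-patient simulation, which "yielded a 95% confidence interval from 0.763 to 1.374". From the nearness of 1.374 to 1.4 it concludes that this "demonstrates that the margin accommodates the variability in the trial design while maintaining sufficient statistical power and clinical importance". No target power and no achieved power is given anywhere.

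**The concern.** The sentence is an affirmative claim about an operating characteristic, and it is offered as support for the margin that decides the primary endpoint. An upper limit just inside the margin is weak evidence of power, because sampling variation alone will often carry the observed limit past the margin even when the regimens are equivalent.

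The consequence is for interpretation. A reader told that power is sufficient will expect equivalent regimens to be declared non-inferior with high probability, and may take a failure as evidence against the single dose. The "Analysis methods" section plans two written interpretations of blinded results before the code is unsealed. Those interpretations need a correct view of how often the trial would miss under true equivalence.

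**Working it through.** **Inputs, all from the SAP.** Margin 1.4 and the two-sided 95% rule; limits 0.756 to 1.323 (10,000 per group) and 0.731 to 1.368 (8,000 per group) at an odds ratio of 1.000; bootstrap limits 0.763 to 1.374; PJI risk 1.2% (1.0% to 1.4%).

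**Step 1: reproduce the printed limits.** For two equal arms with risk p and n per arm, SE(log OR) = √[2 / (n p (1 − p))] and the limits are exp(±1.96 SE). The SAP does not say which risk was simulated. With p = 1.0%:

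- n = 10,000: SE = √[2 / (10,000 × 0.0099)] = 0.1421, limits 0.757 to 1.321.
- n = 8,000: SE = 0.1589, limits 0.732 to 1.365.

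In 400,000 simulated pairs of binomial arms at 1.0%, the average Wald limits were 0.756 to 1.323 and 0.731 to 1.368, which are the printed figures to three decimals. At the SAP's mean risk of 1.2% the formula gives 0.775 to 1.290 and 0.752 to 1.329, which do not match. The printed intervals therefore behave like an overall two-group comparison at a risk of about 1.0%.

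**Step 2: power from the printed limits.** SE = (ln U − ln L) / 3.92, and power = Φ[(ln 1.4 − ln OR) / SE − 1.96], with ln 1.4 = 0.3365.

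| Interval | SE | Power, true OR 1.0 | Power, true OR 1.05 |
|---|---|---|---|
| 10,000 per group, 0.756–1.323 | 0.1428 | Φ(0.397) = 65.4% | 52.2% |
| 8,000 per group, 0.731–1.368 | 0.1599 | Φ(0.145) = 55.8% | 43.6% |
| Bootstrap width, 0.763–1.374 | 0.1501 | Φ(0.282) = 61.1% | – |

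At a true odds ratio of 1.0 the trial would miss in about 35% of repetitions (10,000 per group) or 44% (8,000 per group).

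**Step 3: test the proximity argument itself.** The same power can be written as Φ[(ln 1.4 − ln U) / SE], where U is the expected upper limit. If U = 1.4 this is Φ(0) = 50%. If 1.374 is taken as the expected upper limit, it is Φ(ln(1.4/1.374) / 0.1501) = Φ(0.0187 / 0.1501) = Φ(0.125) = 55%.

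**Step 4: vary the infection risk.** Simple binomial variance, true OR 1.0:

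| PJI risk | SE (10,000 / 8,000) | Power (10,000 / 8,000) | Simulated power |
|---|---|---|---|
| 1.0% | 0.1421 / 0.1589 | 65.8% / 56.3% | 65.7% / 56.1% |
| 1.2% | 0.1299 / 0.1452 | 73.6% / 64.0% | 73.4% / 64.0% |
| 1.4% | 0.1204 / 0.1346 | 79.8% / 70.6% | 79.6% / 70.5% |

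Only the most favourable combination, the top of the risk interval with the full 10,000 per group, comes close to the customary 80%.

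**The case against.** The SAP disclaims a formal power calculation, names no target and prints no power figure, so there is no wrong number to correct, only an unsupported adjective. That is right, and it limits the finding to a misleading claim. It does not rescue the claim: a plan that reports no power calculation cannot also say that sufficient power has been demonstrated.

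The practical consequence is limited. Recruitment closed on 30 November 2024, the sample size was set by patient flow, and the result will be judged by its interval against 1.4. This also stands. What remains is how a failure to meet the margin would be read.

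The 65% and 56% are conditional. They correspond to a risk of about 1.0%, the bottom of the SAP's interval, and power is higher at 1.2% or 1.4%. That is why the range is shown.

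The bootstrap figure is weak support. Its interval has geometric centre √(0.763 × 1.374) = 1.024 and may reflect one simulated data set, so 1.374 is not the expected upper limit at an odds ratio of 1.0; the SAP's figure for that is 1.323. I accept this. The main result uses the simulated intervals, and the point also undercuts the SAP's own use of 1.374.

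Finally, the SAP does not say which contrast of its group-by-period model the limits describe. The overall group effect is the plausible reading. A single-period contrast with 5,000 per arm would need 2 / (5,000 × p(1 − p)) = 0.1428², so p of about 2%, outside the SAP's 1.0% to 1.4%.

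**Conclusion.** The concern holds. Nearness of an upper limit to the margin does not demonstrate power, and the SAP's own intervals do not support the conclusion it draws. This is an unsupported property used to justify the decision margin, not a missed target. The sizes found in the check rest on a normal approximation on the log odds ratio scale and on reading the printed limits as those of the overall group effect. The binomial range also ignores the centre and period terms of the planned model. The fault in the reasoning depends on none of these assumptions. The correction should be made because it bears on how the primary result is interpreted, but the analysis can run as specified without it.

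**What to change.** Delete the sentence that argues from the proximity of 1.374 to 1.4, including its reference to sufficient power. Replace it with text such as:

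> No formal power target was set. For a margin of 1.4 and a true odds ratio of 1.0, the simulated intervals, taken as limits for the overall group effect, imply about 65% power with 10,000 per group and about 56% with 8,000 per group. With simple binomial variance and a PJI risk of 1.0% to 1.4%, power is about 66% to 80% and 56% to 71% respectively (74% and 64% at 1.2%).

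The contrast and the event risk used in the simulations should be stated beside the printed limits. If the simulation output is still available, the proportion of runs with an upper limit below 1.4 gives the power under the planned model directly and could replace the approximate figures.

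The cost is SAP wording only. Margin, model, enrolment and success rule are unchanged. The only drawback is that the stated property looks less favourable.
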